### 5.2. General Considerations

Categorical variables will be summarized using counts and percentages.

Continuous variables will be summarized using the following descriptive summary statistics: number of patients (n), mean, SD, median, interquartile range (Q1, Q3), minimum value (min), and maximum value (max). The precision of the measurement for each continuous variable will be used to determine the number of decimal places to present in tables, figures and derived listings. Minimum and maximum values will be reported with the same precision as the units of measure. The mean, median, SD, Q1 and Q3 will be reported to one greater decimal place. Any values that require transformation to standard units (metric or SI) will be converted with the appropriate corresponding precision.

The day of the first dose of study drug administered is defined as Day 1. Study Day is defined as the number of days between the day of the first dose of study drug (Day 1) and the specific time point. The Study Day of a time point of interest is calculated as follows.

If after Day 1, Study Day = date of interest - date of the first dose of study drug + 1

If prior to Day 1, Study Day = date of interest - date of the first dose of study drug

Study days are negative when the time point of interest is prior to Day 1, positive when time of interest is after Day 1. There is no Day 0. For example, the day before the first study drug dose is defined as Day -1.

For ALA, PBG and urinary creatinine, the assessments collected and recorded as lower than the lower limit of quantification/detection will be replaced by half of the lower limit of quantification/detection. For other safety laboratory parameters, the assessments collected and recorded as lower than the lower limit of quantification/detection will be replaced by the lower limit of quantification/ detection. Any assessment collected and recorded as greater than the upper limit of quantification will be replaced by the upper limit of quantification.

For all analysis sets except for the All Givosiran Treated Set, summaries will be presented by treatment arm (givosiran and placebo).

For the All Givosiran Treated Set, summaries will be presented by the following groups:

- Givosiran/Givosiran: all patients who received givosiran during the 6m-DB including patients who continued to receive givosiran during the OLE period and patients who discontinued treatment during the 6m-DB period;
- Placebo/Givosiran: all patients who received placebo during the 6m-DB period and switched to givosiran in the OLE period;
- All Givosiran: all patients who received at least one dose of givosiran during either 6m-DB or OLE period.

### 5.3. Computing Environment

All statistical analyses will be performed using validated SAS statistical software Version 9.4 (or later), unless otherwise noted. Figures may be generated using R version 3.4 (or later).

### 5.4. Baseline Definitions

For ALA, PBG, and ALAS1 mRNA, collection of the screening urine samples must occur when the patient is not having an attack, and  $\geq 4$  days after prophylactic hemin discontinuation and after their last hemin dose. Two screening urine samples (collected on 2 different days) should be collected for ALA/PBG; one screening urine sample should be collected for ALAS1 mRNA. On Day 1 visit, before the first dose of study drug is administered, the third urine sample for ALA/PBG is scheduled to be collected. If a patient is having an attack or it has been less than 4 days after the last hemin dose on Day 1, the third urine sample will not be collected on Day 1 and will be postponed until at least 4 days after the last hemin dose. The baseline creatinine normalized ALA/PBG/ALAS1 values will be defined as the median of measurements taken on or prior to Day 1. Any samples taken during an attack or within 3 days after receiving hemin on or prior to Day 1 will be excluded from the baseline calculation. For a patient, if all available samples on or prior to Day 1 meet the exclusion criteria, the last non-missing value on or prior to Day 1 will be used as the baseline value for the patient.

Daily worst scores in pain, nausea and fatigue, as well as analgesic medication use at home, are collected using an electronic diary (eDiary) by patients or caregivers. During the Screening period, the eDiary variables are collected when patients are not experiencing a porphyria attack. For each eDiary variable collected in the Screening period, the average of a minimum of 4 days and a maximum of 7 days (consecutive days not required) is defined as the baseline value. If there are more than 7 days collected for any variable, the measurements closest to Day 1 will be used. All measurements used for the baseline value must be taken when a patient is not experiencing a porphyria attack. If a patient has less than 4 days of measurements on non-attack days prior to Day 1, the average of the available non-attack days will be used for the baseline value.

For all other measures, baseline will be defined as the last non-missing value available on or prior to the first dose of study drug, unless otherwise specified.

For the All Givosiran Treated Set, baseline for patients who switched from placebo to givosiran will be redefined as the values prior to the first dose of Givosiran. For ALA, PBG, and ALAS1 mRNA, the redefined baseline will be calculated as the median of all values after the first dose in the 6m-DB period and prior to the first dose in the OLE period, excluding samples during an attack or within 3 days after receiving hemin. For all the other endpoints, the redefined baseline will be derived in the similar way as described above for the baseline for the 6m-DB period.

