- ^s Blood samples for PK analysis will be collected in all patients at the time points listed in Table 8. An additional 24-hour (± 2 hour) PK assessment (with paired ECG measurement) will be performed on Day 1 and Month 6 in approximately 24 patients from preselected study centers. In patients at East Asian study centers (in Japan, South Korea, or Taiwan), blood samples for PK analysis will be collected at the time points listed in Table 9 (which includes all those time points listed in Table 8).
- ^t In patients at East Asian study centers, spot (predose) and pooled (postdose) urine samples will be collected for PK analysis on Day 1 and Month 6 at the time points listed in Table 10.
- ^u QOL questionnaires to be completed include SF-12, EQ-5D-5L, and days of missed work/school.
- ^v The PGIC assesses a patient's perceived overall health status change since the beginning of the study using a single-item scale.
- ^w The PPEQ is a set of questions to assess treatment experience and impacts to the patient's life that are not collected by the other QOL assessments.
- ^x During the screening period, patients and caregivers will record a minimum of 4 days of eDiary entries for pain, nausea, fatigue, and analgesic use to provide a baseline. These baseline entries must be collected on days when the patient is not experiencing a porphyria attack. During the treatment period through the Month 12 visit, eDiary entries for pain, nausea, fatigue and analgesic use will occur daily. Potential porphyria attacks will be reported in the eDiary when they occur throughout the duration of the study (from screening through the EOS visit). eDiary training will be completed at the study center at Screening. Further details on eDiary training can be found in the Study Manual.
- ^y Serious adverse events (SAEs) will be collected starting at the time that informed consent is signed and through the duration of the study; AEs will be collected starting at the time the first dose of study drug is administered (Study Day 1) through the duration of the study

Table 2: Schedule of Assessments – Open-Label Extension Period: After Month 6 through Month 18

Study Visit (M)	Open-Label Extension Period ^a (After Month 6 through Month 18)									
	Month 6.5	Month 7	Month 8	Month 9	Month 10/11	Month 12	Month 13 ^b /14	Month 15	Month 16/17	Month 18

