The biomarker endpoints include the ALA levels in AIP patients ( $FAS_{AIP}$ ) at 3 months and 6 months, the urinary PBG levels in AIP patients ( $FAS_{AIP}$ ) at 6 months. Any postbaseline ALA/PBG values measured within 3 days after hemin use during the 6m-DB period will be treated as missing and excluded from analysis. For each biomarker secondary endpoint, the biomarker levels at the specified time point will be estimated and compared between two treatment arms using an MMRM model. The model will include baseline of the corresponding biomarker level as a continuous covariate, stratification factors (prior hemin prophylaxis status and historical attack rates), visit, treatment, and visit by treatment as fixed effects, and patient as a random effect. An unstructured covariance matrix will be used to model the within-subject error. If the fit of the unstructured covariance structure fails to converge, a compound symmetry covariance structure will be used. The least squares (LS) means and the corresponding SEM and 95% CIs for each treatment arm, along with the LS mean difference between two treatment arms at each post-baseline visit will be presented. The p-value for the treatment difference for each endpoint (ALA at Month 3 and Month 6; PBG at Month 6) will be presented. In addition, the overall p values measuring the average treatment effect on ALA and PBG during the entire 6m-DB period will also be reported to assess the durability of the treatment effect. If normal assumptions are violated, a non-parametric Wilcoxon rank sum test will be performed. For ALA at Month 3 and Month 6, if the drop-out rate during the 6m-DB period is  $\geq 5\%$  on the givosiran arm, sensitivity analyses will be performed using a PMM approach as described in Section 9.3.

Daily worst scores for pain measured by BPI-SF in Numeric Rating Scale (NRS), fatigue measured by BFI-SF in NRS, and nausea measured by NRS are collected through eDiary. For each of the symptoms (pain, fatigue and nausea), daily eDiary entries will be averaged into a weekly (i.e. 7 day) score. The change from baseline in weekly mean scores is defined as the post-baseline weekly mean score minus the baseline score. The AUC of change from baseline over 6 months in the respective measure will be calculated for each patient based on change from

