### **6.5.3. Exploratory Endpoints**

The continuous exploratory endpoints in AIP patients for the 6m-DB period including EQ-5D-5L index score will be analyzed using an MMRM model similar to the one employed for the secondary endpoint PCS SF-12.

Patient Global Impression of Change (PGIC) at Month 6 and Month 12 will be summarized descriptively with number and proportion of patients in each category, as well as the two combined categories of “Improved” and “No Change or Worsening”. The category of “Improved” includes minimally improved, much improved, and very much improved. The category of no change or worsening includes no change, very much worse, much worse, and minimally worse. Mantel Haenszel chi-square test will be used to compare the proportion of “Improved” between the two treatment arms. Odds ratio will be estimated.

Missed days of work/school in the past 4 weeks at Month 6 will be summarized descriptively.

Porphyria Patient Experience Questionnaire (PPEQ) will be summarized descriptively.

For endpoints assessed in patients with any AHP (FAS) over the 6m-DB period, the analyses will be conducted using methods similar as those employed for the AIP patients (FASAIP).

For EQ-5D-5L, a categorical summary of the numbers and percentages of patients reporting each ordinal response within each EQ-5D domain will also be presented.

Analgesic medication use during the 6-month DB period will be summarized as follows:

- Number (%) of patients who took at least one analgesic medication by category (opioid, non-opioid, either opioid or non-opioid) and PT during periods of screening, Month 1 to 3, Month 4 to the end of 6m-DB period, and during the 6m-DB period.
- Descriptive summary on proportion of days with analgesic use during the 6m-DB period by category (opioid, non-opioid, either opioid or non-opioid).

Refer to Appendix 9.5 for the detailed rules in categorizing analgesic medication and opioid/non-opioid.

Data collected during the OLE period will be summarized descriptively. For daily worst pain/nausea/ fatigue scores collected during the OLE period, change from baseline in weekly mean scores will be summarized descriptively.

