For the secondary endpoints daily worst score of pain, nausea, and fatigue, the AUC over 6 months will be derived by first calculating the weekly mean scores (Section 6.5.2).	Updated to address regulatory feedback on missing data handling and justification of AUC method.

## 7.2. Changes in SAP Amendment 2

In the SAP Amendment 2, detailed analyses for the entire study including OLE period are added. Amendment 2 will be signed off before the final analysis of the 6-month double-blind (6m-DB) data and the unblinding of treatment assignments.

In this version, a new analysis population All Givosiran Treated Set is added, additional subgroups of the All Givosiran Treated Set were defined to accommodate analysis of the different givosiran doses allowed in the OLE period with Protocol Amendment 3, and different treatment periods are defined to allow for the analysis of data in the overall study. In addition, Per Protocol Set is defined to allow for an evaluation of the primary endpoint in the subset of patients who fulfill the protocol in terms of the eligibility requirements, adherence to the study drug and outcome assessments. A few minor updates are made to the analysis of the 6m-DB period, e.g., zero-inflated negative binomial regression model is added to analyze components of attacks. For the analysis of worst scores of pain, fatigue, and nausea, the following updates are made:

- The AUC of weekly scores is updated as the AUC of change from baseline in weekly scores. Note that with an ANCOVA analysis adjusted for baseline, using the actual score or change from baseline as a response variable will yield the same estimate of treatment difference and p value. This update is made to allow for a direct estimate of the LS mean change from baseline in each treatment arm.
- The mean weekly score change from baseline over 6 months is defined for analysis, which is mathematically similar to the AUC of change from baseline in weekly score but is clinically meaningful and interpretable.
- The testing order of daily worst scores of fatigue and nausea are switched because the mean nausea scores at baseline are low therefore less likely to show improvement with treatment.

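### The diary baseline leaves out attack days that follow-up keeps, so within-arm and open-label change in pain, fatigue and nausea understates improvement; the randomised comparison is unaffected

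*SAP*

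**What the plan says.** - **Baseline.** SAP Section 5.4 takes the average of 4 to 7 screening diary days, or fewer if fewer are available, and adds: "All measurements used for the baseline value must be taken when a patient is not experiencing a porphyria attack". There is no fallback to attack days. Protocol Table 1, footnote x, agrees: "These baseline entries must be collected on days when the patient is not experiencing a porphyria attack".
- **Follow-up.** In SAP Section 6.5.2, "daily eDiary entries will be averaged into a weekly (i.e. 7 day) score", and attack days are not excluded. The same section expects symptoms to rise in attacks and gives capturing those peaks as a reason for the AUC. A missing attack week with no attack-day entry is filled from the patient's other attack weeks, or failing that from the worst week.
- **Subtraction.** "The change from baseline in weekly mean scores is defined as the post-baseline weekly mean score minus the baseline score" (SAP Section 6.5.2).
- **Why change is reported.** SAP Section 7.2 explains the move from the score itself to its change: "This update is made to allow for a direct estimate of the LS mean change from baseline in each treatment arm". It also presents the mean weekly change as a quantity that can be interpreted clinically.
- **Open-label extension (OLE).** For these scores, "change from baseline in weekly mean scores will be summarized descriptively" (SAP Section 6.5.3). There is no control arm.
- **Patients switching from placebo.** "For all the other endpoints, the redefined baseline will be derived in the similar way as described above" (SAP Section 5.4).

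Neither document mentions the difference between the two kinds of day or corrects for it.

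**The concern.** The two sides of the subtraction are different quantities: a level between attacks, and an average over all days. A patient whose attack rate and symptoms do not change at all will show a positive change, which reads as worsening. A patient whose only benefit is fewer attacks cannot show a negative change, because the attack days that were relieved were never in the baseline.

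This matters wherever change is read without a comparator. That means the LS mean change in each arm, which is the stated purpose of the Amendment 2 update, and the diary summaries in the OLE.

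**Working it through.** **1. The plan's own figure.** The documents give no expected value or power for the diary endpoints. The only stated figure that uses the same attack rates is the primary power in SAP Section 5.1. Inputs are 6-month means of 4 and 2.2, dispersion k = mean²/(SD² − mean) = 64/17 = 3.76 and 19.36/4.6 = 4.21, and 35 patients per arm.

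SE² = [(1/4 + 1/3.76) + (1/2.2 + 1/4.21)]/35 = 0.0345, so SE = 0.186. Then |ln 0.55|/SE − 1.96 = 1.26, which gives power of 89.6%. With 15% dropout it is 84.3%. These agree, to rounding, with the stated 90% and are above the stated 80%.

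**2. The offset.** Let c0 and c1 be the mean score between attacks before and after baseline, f0 and f1 the share of days in attack, and D the rise on attack days.

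- SAP change = (c1 + f1·D) − c0
- All-days change = (c1 + f1·D) − (c0 + f0·D)
- Offset = SAP change − all-days change = f0·D

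Only the pre-treatment share f0 enters, so randomisation makes the expected offset equal in the two arms.

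**3. Size.** f0 = attacks per year × days per attack / 365.25. The rate of 8 is the plan's placebo assumption, taken here as the pre-treatment rate. The rate of 10.5 is 8/0.76, because Protocol Section 1.3 puts the composite at about 76% of all attacks. Attack length and D are assumed.

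| Attacks/year | Days per attack | D (points) | f0 | Offset (points) | Over 24 weeks (point-weeks) |
|---|---|---|---|---|---|
| 8 | 3 | 3 | 6.6% | 0.20 | 4.7 |
| 8 | 5 | 4 | 11.0% | 0.44 | 10.5 |
| 8 | 10 | 5 | 21.9% | 1.10 | 26.3 |
| 10.5 | 5 | 4 | 14.4% | 0.58 | 13.8 |

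A wider grid (4 to 12 attacks a year, 3 to 10 days, 2 to 6 points) gives 0.07 to 1.97 points.

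**4. A patient who benefits only through fewer attacks.** Suppose attacks fall from 8 to 4.4 a year, with 5 days and 4 points. The SAP change is 4.4 × 5/365.25 × 4 = +0.24. The all-days change is 0.24 − 0.44 = −0.20. If attacks stop altogether, the SAP change is 0 and the all-days change is −0.44.

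**5. Day-level simulation.** This used 35 patients per arm, 168 days, weekly means, 5-day attacks, D = 4 and 1,000 runs. Change is in NRS points.

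| Givosiran scenario (placebo stable at 8/year) | Placebo, SAP baseline | Givosiran, SAP baseline | Difference | Givosiran, all-days baseline | Difference, all-days |
|---|---|---|---|---|---|
| 8/year | +0.41 | +0.41 | 0.00 | 0.00 | 0.00 |
| 4.4/year | +0.41 | +0.23 | −0.18 | −0.18 | −0.18 |
| 4.4/year and 0.5 lower between attacks | +0.41 | −0.27 | −0.68 | −0.68 | −0.68 |

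The offset is 0.41, not 0.44, because overlapping attacks count once. In the first row the test rejected in 4.1% of runs without the baseline score as covariate and in 4.4% with it, against a nominal 4.9% (Monte Carlo standard error √(0.049 × 0.951/1000) = 0.7 percentage points). Both models were run because SAP Section 6.5.2 lists only treatment and the two stratification factors, while Section 7.2 speaks of adjusting for baseline. The conclusion does not depend on which is meant.

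**The case against.** The attack-free baseline is deliberate and stated in both documents. With only 4 to 7 days, admitting attack days would make baseline depend on whether an attack happened to fall in that short window. Keeping the peaks in follow-up is also justified in the text. This stands, and it is why the baseline rule itself should not be changed. An all-days screening baseline may not be recoverable anyway, since screening entries are meant for attack-free days.

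Little that is confirmatory depends on the point. The tested comparison is between arms. OLE diary results are descriptive, and daily scores stop at Month 12. Attack reduction in switching patients is measured directly by the intra-patient comparison of attack rates in SAP Section 5.10. The offset also works against the drug, so it cannot create an apparent benefit. All of this stands. It limits the point to presentation, but does not remove it, because Section 7.2 adopted change from baseline in order to report it by arm.

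The size is uncertain. A patient with no attack days before treatment has no offset, and attack-day entries missing from an otherwise completed week shrink it without reversing it.

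A reader might go further in two ways that the documents do not support:

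- **An offset of 0.24 on givosiran against 0.44 on placebo.** The rate of 4.4 is the assumed treated rate, so a patient at that rate has changed. The artefact sits in the baseline and is equal in both arms.
- **The redefined ALA/PBG baseline as a precedent for an attack-inclusive diary baseline.** SAP Section 5.4 does use the whole placebo period there, but it leaves out samples taken in an attack or soon after hemin.

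**Conclusion.** The point holds for within-arm and OLE change. The direction follows from the SAP's own definitions and its expectation that symptoms rise in attacks. The offset is +0.44 points in the central case and +0.20 to +1.10 over the stated range. These figures rest on 8 attacks a year before treatment and on assumed attack length and rise, so they show scale only.

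It would be wrong to infer that the randomised test is biased: the between-arm difference is the same under either baseline, and rejection under the null stays near nominal. Nor is it right that fewer attacks earn no credit at all. The change does fall (from +0.44 to +0.24 in the example), but it cannot go below zero on that account alone.

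For patients switching from placebo, carrying over the attack-free rule is the most natural reading of "For all the other endpoints, the redefined baseline will be derived in the similar way as described above", but the SAP does not spell it out for diary data.

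**What to change.** 1. Keep the AUC ANCOVA as the between-arm test. Label arm-level change, in the double-blind period and the OLE, as relative to an attack-free baseline. Add the change in mean score on non-attack days against that baseline, which compares like with like. Report the attack-inclusive result as absolute weekly mean scores per arm plus the between-arm difference.
2. For patients who move from placebo to givosiran, state which days form the redefined diary baseline. Add a supplementary within-patient comparison of attack-inclusive weekly means in the placebo period against the OLE. Show it for the Placebo/Givosiran group only. Pooling it into the All Givosiran column would mix two definitions of change.

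The data are already collected: attacks are recorded by calendar day (SAP Section 6.5.1.4), and daily scores run through Month 12 (Protocol Sections 7.2.2 and 7.2.3). The cost is SAP wording and one more set of diary tables to explain. The confirmatory analysis does not change.
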